This prospective controlled study will use machine learning and other information technologies to analyze clinical data from AIIRD patients. By fitting early clinical indicators (e.g., symptoms, laboratory results) with PJP infection and outcomes, combined with our center's predictive model (combination factor 1 = IgA – IgM × 2.072/1.411) and international consensus and expert recommendations on PJP prophylaxis [11-17], we aim to establish new screening criteria for high-risk populations, and stratified analysis was performed based on risk factors. We'll assess the efficacy

and safety of prophylactic treatment (TMP/SMZ) for PJP in AIIRD patients, explore the AIIRD populations that benefit the most from prophylactic treatment and evaluate the benefit-risk ratio of prophylactic treatment in AIIRD patients, aiming to achieve early identification and guidance for prophylactic treatment, ultimately reducing PJP incidence and improving outcomes in AIIRD patients.

Objectives

1. Develop and validate a predictive model for PJP infection risk in AIIRD patients to facilitate risk stratification, enhanced monitoring, and early prophylactic treatment.
2. Investigate the impact of prophylactic treatment on the incidence and outcomes of PJP in AIIRD patients, evaluating the efficacy, safety, and benefit-risk ratio of prophylactic treatment.

Study design

This study will prospectively collect peripheral blood, respiratory specimens, and clinical data from AIIRD patients, analyze the biological data, establish clinical prediction models, identify high-risk PJP populations among AIIRD patients and administer prophylactic trimethoprim-sulfamethoxazole (TMP/SMZ) treatment. The efficacy and clinical utility of the PJP infection risk prediction model will be validated, and the impact of prophylactic anti-PJP treatment on incidence and outcomes will be explored.

Selection of AIIRD patients

1. Inclusion criteria

- a) Diagnosed with AIIRD according to international classification criteria and receiving corticosteroid or immunosuppressant therapy;
- b) No prior standard PJP treatment, including first-line TMP/SMZ or other

second-line treatments;

- c) Age \geq 18 years;
- d) Informed consent signed for biological sample collection.

2. Exclusion criteria

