a) Prospectively, we group AIIRD patients into high-risk and low-risk based on the prediction model, and they are further divided into 4 groups according to the intention-to-treat principle: high-risk group 1 (Patients intend to treat with prophylactic TMP/SMZ), high-risk group 2 (Patients intend to treat without prophylactic TMP/SMZ), low-risk group 1 (Patients intend to treat with prophylactic TMP/SMZ), low-risk group 2 (Patients intend to treat without prophylactic TMP/SMZ).

c) Trimethoprim-sulfamethoxazole intervention regimen: TMP/SMZ 480mg po qd (one tablet per day, oral); Treatment time: routine ≥ 28 days (according to the needs of the patient's condition, as well as the patient's tolerance to the drug and the willingness to treat, the clinician will adjust the time).

4. Follow-up and data collection

a) Establish a long-term follow-up to collect each clinical data on a regular basis.

Study visits were set at baseline, 6 and 12 months after the initiation of treatment. The

end points of follow-up were PJP infection, occurrence of serious side effects, death, loss to follow-up, end of follow-up, or withdrawal from the study. Main outcome indicator is pneumocystis infection incidence, and secondary indicators include TMP/SMZ related adverse events, PJP related mortality, other prognostic indicators and parameters of the respiratory system.

5. Statistics and data analysis

- a) Using difference test statistical analysis methods such as comparing two main outcome indexes between the groups of patients. Possible confounding factors, such as age, gender, and baseline conditions, were considered in the analysis, and covariates were adjusted if necessary.
- b) Statistical analysis methods (such as ROC curve, calibration plot, DCA curve, etc.) were used to evaluate the prediction model performance and visual display (Nomogram, etc.).
- c) Stratified according to risk factors, the absolute risk difference of PJP between the control and prevention groups was calculated, and the NNT was calculated based on the risk difference. The bootstrap method is used to estimate NNT and NNH 95% confidence interval (95% CI), for different people to undergo preventive SMZ/TMP risk-benefit assessments.

Possible risks and preventive measures

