- a) Possible risks: (1) When peripheral blood samples are obtained from patients, some patients may have dizziness and other symptoms due to their physical weakness. (2) When obtaining induced sputum or bronchoalveolar lavage fluid from patients, some patients may have the risk of bronchospasm and asthma induction because they cannot tolerate it. (3) Adverse reactions of TMP/SMZ (such as rash, fever, purpura, nausea and vomiting, leukopenia, elevated transaminase, etc.) occurred during the treatment.
- b) Preventive measures: (1) Professional medical staff should take care of the blood collection place, assess whether the patient's current health status is suitable for

additional blood collection, and pay close attention to the patient's status during blood collection. The corresponding first aid drugs are stored at the blood collection site for a long time. (2) The respiratory specimen collection place will be attended by professional medical staff, who assessed whether the patient's current health status is suitable for respiratory specimen collection, and pay close attention to the patient's status during the collection process. The corresponding first aid drugs are stored at the collection place for a long time. (3) Follow up the patients' symptoms and signs regularly, and ask them to check the complete blood count, liver and kidney function, and electrolytes regularly. The TMP/SMZ should be stopped at the first appearance of rash or any signs of adverse reactions, and the adverse reactions should be treated with symptomatic treatment (such as anti-allergic, kidney protective, liver protective drugs; If is showing signs of bone marrow suppression, should be given to patients every day leucovorin 5-15 mg, until the hematopoietic function returned to normal, if necessary, can be used to promote red, white needle and boost platelet hormone therapy).

Reference

- [2] Sepkowitz K A. Opportunistic infections in patients with and patients without acquired immunodeficiency syndrome[J]. *Clinical infectious diseases*, 2002, 34(8): 1098-1107.

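### A serious side effect is listed as ending follow-up, so PJP after a serious TMP/SMZ reaction is not counted, although groups are formed by intention to treat

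*Protocol*

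**What the plan says.** All references are to the Protocol.

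- **Study process, 4. Follow-up and data collection, a):** "end points of follow-up were PJP infection, occurrence of serious side effects, death, loss to follow-up", and the list goes on to the end of follow-up and study withdrawal. The next sentence names the outcomes. PJP incidence is the main one, and "secondary indicators include TMP/SMZ related adverse events, PJP related mortality, other prognostic indicators". The schedule is fixed: "Study visits were set at baseline, 6 and 12 months after the initiation of treatment".
- **Study process, 3. Grouping and Experimental Intervention, a):** patients at high and at low risk are "divided into 4 groups according to the intention-to-treat principle", that is, by whether TMP/SMZ is intended or not.
- **Possible risks and preventive measures, b) (3):** "The TMP/SMZ should be stopped at the first appearance of rash or any signs of adverse reactions".
- **Study process, 5. Statistics and data analysis, c):** "the absolute risk difference of PJP between the control and prevention groups was calculated", and the NNT is derived from it.

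Nothing in the Protocol provides for PJP ascertainment after a serious side effect.

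**The concern.** A comparison by intended treatment needs PJP counted in the intended group whether or not the drug is later stopped. PJP that follows a forced stop is part of what happens when prophylaxis is chosen. Here the drug stop and the end-point list act together: a treated patient with a serious reaction loses prophylaxis and, as written, leaves the PJP count at the same moment. What remains visible in the treated groups is mostly time under protection.

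At stake are the risk difference and NNT, and with them the benefit-risk assessment in Objective 2. If serious side effects are more frequent with TMP/SMZ than without, the loss of events is one-sided and the results favour prophylaxis. PJP is rare, so few events carry the comparison. If observation really stops, no later analysis plan can recover the missing events.

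**Working it through.** **1. Reading the list.** Loss to follow-up, end of follow-up and withdrawal are not outcomes; they are ways in which observation ends. The outcomes have their own sentence. The plain reading is therefore that each listed event ends a participant's follow-up for PJP. The Protocol gives no figure for this point, so there is none to reproduce; what follows is an illustration.

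**2. Inputs.**
- From the Protocol: untreated PJP risk p = 0.7% to 2% (Background), taken here as a 12-month risk; last visit at 12 months, T = 365 days; routine course of at least 28 days (Study process, 3 c).
- Assumed: N = 400 treated (half of the planned 800); 85% protection on drug and none after; serious side effect at t = 14 days in x = 2% to 10% of treated patients and in y of untreated patients; course of D = 28 or 365 days; risk spread evenly over time.

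**3. Expected PJP cases missed among the treated** = N × x × p × (T − t)/T

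| | x = 2% | x = 5% | x = 10% |
|---|---|---|---|
| p = 0.7%, t = 14 | 0.05 | 0.13 | 0.27 |
| p = 2%, t = 14 | 0.15 | 0.38 | 0.77 |
| p = 0.7%, t = 90 | 0.04 | 0.11 | 0.21 |
| p = 2%, t = 90 | 0.12 | 0.30 | 0.60 |

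For example, 400 × 0.05 × 0.02 × 351/365 = 0.38. Every entry is below one case.

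**4. Effect on the NNT, p = 2%, x = 5%, D = 365.**
- Treated, not cut off: p(1 − 0.85 D/T) = 0.02 × 0.15 = 0.300%.
- Affected, fully followed: p[0.15 t/T + (T − t)/T] = 0.02 × (2.1 + 351)/365 = 1.935%.
- Affected, observed only to day 14: p × 0.15 t/T = 0.0115%.
- Treated risk, full follow-up: 0.95 × 0.300% + 0.05 × 1.935% = 0.382%, or 1.53 cases per 400.
- Treated risk, counted as PJP-free after the cut: 0.95 × 0.300% + 0.05 × 0.0115% = 0.286%, or 1.14 cases per 400.
- Untreated risk observed: p[(1 − y) + y t/T].
- With time-to-event censoring, the treated estimate is the 0.300% of those not cut off.

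The same formulas with D = 28, and with p = 0.7%, give:

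| NNT | Full follow-up | y = 0 | y = 2.5% | y = 5% | Censored |
|---|---|---|---|---|---|
| p = 2%, D = 365 | 61.8 | 58.3 | 60.0 | 61.8 | 58.8 |
| p = 0.7%, D = 365 | 177 | 167 | 171 | 177 | 168 |
| p = 2%, D = 28 | 786 | 448 | 571 | 786 | 767 |

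In the first row, about a quarter of the expected treated cases are lost (0.38 of 1.53). When both groups are cut off equally often, the NNT does not move. The large shift in the last row needs a 28-day course, cut-off patients counted as PJP-free, and cut-offs that are rarer or absent among the untreated, all together.

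**5. A second set of assumptions.** Take an on-drug relative risk of 0.1 to 0.3, serious side effects in 2% to 10% of treated patients at month 1, a full course otherwise, and no cut-offs among the untreated. The share of treated cases missed then runs from 6% to 50%. At 2% untreated risk, the smallest NNT shift is from 56.6 to 55.4 and the largest from 78.6 to 68.7.

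**The case against.** The list cannot be literal throughout. It includes PJP infection, yet PJP-related mortality is an outcome and needs observation after PJP; it also includes the end of follow-up itself. One could read it as events to be recorded, in which case later PJP still counts. The Protocol does not say that visits or data collection stop, and regular checks of symptoms and blood tests after reactions suggest continued contact. The intention-to-treat phrase labels the groups and does not commit the analysis. The drug stops for any reaction, but only serious ones are on the list, so most patients who stop may be unaffected. The item is also not limited to TMP/SMZ: every participant is "receiving corticosteroid or immunosuppressant therapy", so untreated patients can meet it too. Finally, the effect is tiny beside sampling error. With risks of 2% and 0.382% and 400 per group (assumed), the standard error of the 1.618% difference is 0.765%, and the 95% interval for the NNT runs from about 32 to 840.

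Much of this stands as a limit on size and certainty. The direction of bias is plausible, not established, and only the serious subset is affected. The alternative reading is the weaker one, because loss to follow-up and withdrawal do not fit a list of events to record and no sentence restores PJP follow-up. Even if full follow-up is intended, a site following the text could stop collecting PJP data.

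**Conclusion.** The concern holds. As written, PJP after a serious side effect falls outside the count, which is at odds with grouping by intended treatment and, if such events are commoner on TMP/SMZ, favours prophylaxis. The expected loss is below one case per 400 treated in every scenario in step 3, and for a 12-month course the NNT shift is modest (58 against 62 at 2% incidence and 5% affected). Only the 0.7–2% incidence, the 12-month horizon and the 28-day minimum course come from the Protocol; reaction rate, timing, protection and group size are assumptions. The point should be corrected because the events are few, their loss may be irrecoverable and the repair is cheap. The size alone would not make it critical. Confidence is moderate, since the wording is loose.

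**What to change.** In Study process, 4. Follow-up and data collection, a), remove serious side effects from the events that end follow-up, and keep them as a safety outcome and a reason for stopping the drug. Then add:

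> A participant who stops TMP/SMZ for any reaction, or who has a serious side effect in any of the four groups, stays in the intended-treatment group and is followed for PJP and death at the 6- and 12-month visits; any later PJP prophylaxis is recorded.

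The safety stop rule in Possible risks and preventive measures, b) (3) stays as it is.

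The cost is a short protocol amendment, with no new patients and no new visit dates. With 400 treated and 2–10% affected (assumptions), 8 to 40 people complete up to two existing visits each, at most 16 to 80 visits, plus those of any affected untreated patients. The downside is that PJP after a stop counts against TMP/SMZ, so the estimated benefit is slightly smaller. An on-treatment analysis can be kept as a secondary result.

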Study Protocol

**Efficacy and Safety of Prophylactic
Treatment for *Pneumocystis Jirovecii*
Pneumonia (PJP) in Patients with
Autoimmune Inflammatory Rheumatic
Disease (AIIRD)**

Version date: 2024.07.04

Background

Pneumocystis jirovecii pneumonia (PJP) is an opportunistic infection that occurs in immunocompromised patients. The typical clinical symptoms include fever, cough, and dyspnea, with a rapid onset and progression to hypoxemia and even respiratory failure. PJP can be divided into HIV-associated PJP and non-HIV PJP [1-2]. In recent years, with the increasing use of iatrogenic immunosuppressants, the incidence of PJP in non-HIV patients has risen, particularly among patients with autoimmune inflammatory rheumatic diseases (AIIRD), such as systemic lupus erythematosus, rheumatoid arthritis, inflammatory myopathies, and systemic vasculitis [3]. The incidence of PJP in AIIRD patients ranges from 0.7% to 2%, significantly higher than in the general population [4]. In addition, AIIRD patients with PJP are prone to progress to respiratory failure, with severe symptoms, poor prognosis and high mortality. Early identification and prophylactic treatment of PJP could improve outcomes and reduce mortality [5].

Currently, identifying PJP in AIIRD patients is challenging due to overlapping clinical features, such as fever and lymphopenia, and the reduced detection rates of Pneumocystis in respiratory specimens due to immunosuppressant use. Early warning based on serological markers offers a new approach for identifying PJP in AIIRD patients [6-8]. Although there are guidelines for preventing PJP in HIV patients, hematologic malignancies, and solid organ transplant recipients [9-10], no consensus guidelines exist for AIIRD patients on immunosuppressive therapy. More clinical evidence is needed to develop evidence-based clinical guidelines for prophylactic treatment of PJP in AIIRD patients.

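### The only named mortality outcome, PJP-related death, needs an uncertain attribution, and follow-up as written stops before many of the deaths it should count

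*Protocol*

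**What the plan says.** Objective 2 of the protocol includes "evaluating the efficacy, safety, and benefit-risk ratio of prophylactic treatment". The outcomes are set under Study process, item 4 (Follow-up and data collection): "Main outcome indicator is pneumocystis infection incidence", and the secondary list, which is open, has TMP/SMZ-related adverse events, "PJP related mortality, other prognostic indicators and parameters of the respiratory system". All-cause mortality is not named.

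The sentence just before the outcomes says that the "end points of follow-up were PJP infection, occurrence of serious side effects, death, loss to follow-up, end of follow-up, or withdrawal from the study". Visits are at baseline, 6 and 12 months.

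The Background states that "identifying PJP in AIIRD patients is challenging due to overlapping clinical features", and adds that immunosuppressants lower the detection rate in respiratory specimens. Item 3 forms the four groups by risk and intended treatment. No randomisation, blinding or adjudication of cause of death is described.

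Item 5c defines the quantitative benefit-risk analysis: "the absolute risk difference of PJP between the control and prevention groups was calculated, and the NNT was calculated based on the risk difference", set against an NNH, with bootstrap confidence intervals for both.

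**The concern.** A death enters the named mortality outcome only if PJP was recognised and someone judged that it caused the death. By the protocol's own account the first step is unreliable in these patients, who are also said to be prone to respiratory failure and high mortality. A respiratory death without detection of the organism is then either missed or classified by judgement. Nothing described keeps that judgement from being made with knowledge of whether the patient was on prophylaxis.

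A second problem lies in the follow-up rule. PJP-related death comes after PJP infection, yet PJP infection is listed as an end of follow-up. Serious side effects are listed too, so a death that follows a serious drug reaction also falls after the stated end. At stake is whether the study can say anything reliable about deaths under its second objective.

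**Working it through.** The protocol states no mortality figure to reproduce. The check sets the passages side by side and then sizes the event counts.

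**Step 1: outcome against follow-up rule.**

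| Event sequence | Observed if the rule is read literally? |
|---|---|
| PJP diagnosed in life, death later | No: follow-up ended at PJP |
| Serious side effect, death later | No: follow-up ended at the side effect |
| Death without either event | Yes: death is itself an end of follow-up |
| Respiratory death, PJP unrecognised | Yes as a death, but not in PJP-related mortality unless attributed |

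A looser reading would treat the list as events to be recorded. But it also contains loss to follow-up, end of follow-up and withdrawal, which are not outcomes, and the outcomes are given separately in the next sentence. The list therefore reads as a set of stopping events.

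**Step 2: number of PJP cases.** Inputs from the protocol: N = 800 (Sample size estimation) and incidence 0.7-2% (Background).

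- 800 × 0.007 = 5.6
- 800 × 0.02 = 16

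These are upper counts, as if prophylaxis prevented nothing.

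**Step 3: number of PJP deaths.** Case fatality is not in the protocol; assume 20-50%.

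- All 800 unprotected: 5.6 × 0.2 = 1.1, up to 16 × 0.5 = 8
- Assume 400 without prophylaxis: 400 × 0.007 × 0.2 = 0.56, up to 400 × 0.02 × 0.5 = 4.0
- Assume 400 with prophylaxis and a 90% reduction: 0.056 to 0.4

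In the last scenario the two groups together have 0.6 to 4.4 deaths. One reclassified death is 1/4.4 = 23% of the highest total and exceeds the lowest. Even against 8 deaths it is 1/8 = 12.5%.

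**Step 4: what all-cause mortality could show.** Write m for background mortality (assumed 2-10%), p for PJP incidence and c for case fatality (assumed 30% here). Then p1 = m + p·c without prophylaxis and p2 = m + 0.1·p·c with it. With n = 400 per group, a two-sided 5% test and p̄ = (p1 + p2)/2, the normal approximation is:

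power = Φ{ [ (p1 − p2)√n − 1.96√(2p̄(1 − p̄)) ] / √( p1(1 − p1) + p2(1 − p2) ) }

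| Outcome | p1 vs p2 | Expected deaths per 400 | Power |
|---|---|---|---|
| PJP death, low (p = 0.7%, c = 20%) | 0.0014 vs 0.00014 | 0.56 vs 0.06 | 9% |
| PJP death, high (p = 2%, c = 50%) | 0.010 vs 0.001 | 4.0 vs 0.4 | 41% |
| All-cause, m = 2%, p = 2% | 0.0260 vs 0.0206 | 10.4 vs 8.2 | 7% |
| All-cause, m = 10%, p = 0.7% | 0.1021 vs 0.1002 | 40.8 vs 40.1 | 3% |

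The approximation is rough at such small counts and serves only for scale. All-cause mortality gains freedom from attribution, not power.

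**The case against.** The strongest reply has four parts.

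- **Benefit-risk.** A reader might infer that the benefit-risk comparison itself is biased. The protocol does not support that: item 5c takes the NNT from the PJP risk difference, and mortality does not enter it. Misdiagnosed PJP could distort that NNT, but this is a matter for the main outcome.
- **Fatal drug harm.** A reader might also infer that deaths from TMP/SMZ are left out of the study. They are outside PJP-related mortality, but nothing bars fatal events from the adverse-event outcome or the NNH.
- **Confounding.** Groups follow intended treatment, so all-cause death brings in deaths from underlying disease, whose severity may also influence who receives prophylaxis. That is confounding as well as noise. It is a good reason not to make all-cause death the benefit-risk measure.
- **Open list.** The secondary indicators are not exhaustive, and a statistical analysis plan may add definitions. True, but an unspecified category does not commit the study to all-cause mortality, and the follow-up rule is fixed in the protocol itself.

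The first three limit what may be claimed and how the fix is framed. None of the four resolves the conflict between an outcome of death from PJP and follow-up that ends at PJP.

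**Conclusion.** The point holds for the mortality comparison only. The one named mortality outcome depends on a difficult diagnosis and on attribution with no described safeguard, and the literal follow-up rule leaves unobserved the deaths after PJP and after serious side effects. Because death is on the list of stopping events, it is tempting to say that every death is already recorded; the full sentence shows otherwise.

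The net direction of bias is not established. Suspecting PJP more readily in patients off prophylaxis would favour prophylaxis, while missed PJP deaths, expected mainly in patients off prophylaxis, would understate its benefit. Absence of blinding is inferred from the protocol's silence.

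The size rests on assumed case fatality, group sizes and effect: about 1-8 PJP deaths in 800 unprotected patients, or 0.6-4.4 if half are protected at 90%. At such counts, one attribution or one unobserved death can change the picture. This is an inexpensive improvement to the protocol and leaves the main analysis intact.

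**What to change.** 1. Reconcile the end-of-follow-up rule with the mortality outcome: collect vital status to the existing 12-month visit for all patients, including after PJP, after a serious side effect and after TMP/SMZ has been stopped.
2. Add all-cause mortality to 12 months as a named secondary outcome, with all patients in each intended group as denominator and the same confounder adjustment as the other group comparisons.
3. Report PJP-related mortality beside it on the same denominator.
4. Describe all-cause mortality as an attribution-free safety and consistency check. Leave the PJP-based NNT in place.

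The cost is protocol wording plus a vital-status check at 12 months for patients whose follow-up would otherwise have ended. The added outcome will have low power (about 3-7% in the scenarios examined), and underlying-disease deaths will add noise and possible confounding, so a null difference should not be read as evidence of no effect on survival.

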- a) Significant health issues, including (but not limited to) the following: Patients with severe liver injury (elevated serum aminotransferase (ALT, AST), more than 5 times the normal value), severe renal insufficiency (GFR < 30mL/min or Scr > 445umol/L), severe myelosuppression (Hb < 65g/L, PLT < 25 \times 10⁹/L or neutrophil < 0.5 x 10⁹/L);
- b) Screening of known when infected with human immunodeficiency virus (HIV), over the past five years with lymphoid tissue proliferative disease or any organ system malignant tumor medical history, history of solid organ transplant patients;
- c) History of sulfonamide allergy or folate deficiency-related megaloblastic anemia;
- d) Pregnant and lactating women;
- e) Any medical or psychiatric condition that the investigator believes would prevent the trial participant from adhering to or completing the study according to the protocol;
- f) Patient refused to comply with the requirements of this study to complete the work.

Sample size estimation

It is expected to prospectively collect a total of 800 patients diagnosed with AIIRD in our hospital. Based on the previous literature and the experience data of our center, there were large differences in some tested indicators in some subgroups. Because involved in machine learning, the required number of samples roughly follows the http://blog.csdn.net/uestc_c2_403/article/details/72859021 url provided by the algorithm, which is about 10 times the number of dimensions + 1. Prospective data expected into the analysis of the parameters/index for 70. Considering that about 10-20% of patients may have missing data in real-world practice, the final sample size

for prospective collection was $70*1.2*10 \approx 800$.

Study process

1. Enrollment criteria and patient recruitment

a) Define enrollment criteria and recruit eligible AIIRD patients.

b) Explain the study purpose and obtain written informed consent.

2. Construct a clinical prediction model and recognize PJP high-risk patients

a) The prediction model was established by combining the developed prediction model (combination factor 1= IgA-IgM \times 2.072/1.411) with clinically recognized risk factors (including long-term use of high-dose corticosteroids, combination of immunosuppressants, and pulmonary diseases).

b) According above criteria, AIIRD patients with high risk or low risk of PJP are recognized.

3. Grouping and Experimental Intervention

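### Prophylaxis and control groups are formed by intended treatment with no allocation method stated, yet confounder adjustment is optional and the NNT names no control beyond stratification

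*Protocol*

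**What the plan says.** **Forming the groups** (Protocol, Study process, item 3a). First "we group AIIRD patients into high-risk and low-risk based on the prediction model"; then "they are further divided into 4 groups according to the intention-to-treat principle". Within each risk level the split is between patients intended to receive TMP/SMZ and patients intended not to. No randomisation, allocation ratio or other allocation rule appears anywhere in the protocol.

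**Main comparison** (item 5a). Groups are compared with an unspecified difference test. On confounding the text is: "Possible confounding factors, such as age, gender, and baseline conditions, were considered in the analysis, and covariates were adjusted if necessary".

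**NNT** (item 5c). "Stratified according to risk factors, the absolute risk difference of PJP between the control and prevention groups was calculated, and the NNT was calculated" from that difference, with bootstrap intervals for NNT and NNH. No adjusted risk difference is mentioned.

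**Partial control already in the plan.** Item 2a builds the risk class from combination factor 1 (IgA and IgM) together "with clinically recognized risk factors (including long-term use of high-dose corticosteroids, combination of immunosuppressants, and pulmonary diseases"). The exclusion criteria remove some reasons for withholding the drug: "History of sulfonamide allergy or folate deficiency-related megaloblastic anemia", and severe liver, renal or marrow disease.

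**What depends on it.** Objective 2 is the efficacy, safety and benefit-risk ratio of prophylaxis, which is a causal question.

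**The concern.** The intention-to-treat principle governs how patients are analysed once they have been allocated. Used as a grouping rule, it does not make the groups comparable. If treatment follows a clinical or patient decision, whatever drives that decision may also drive PJP risk. The efficacy result and the NNT would then mix drug effect with baseline risk.

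The protocol recognises confounding but treats adjustment as optional. Followed as written, a crude difference test can be the main answer to Objective 2, and the choice to adjust can be made with outcomes in hand. With few events, one or two cases could settle whether adjustment looks needed. The bootstrap intervals in 5c reflect sampling error only and would not reveal this bias.

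**Working it through.** The protocol gives no effect size, allocation ratio or confounder strength, so it has no figure of its own to reproduce on this point. The check asks how much bias the named stratification could leave, and how that compares with chance.

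**Inputs from the protocol.** Planned total 800 (Sample size estimation; the product printed there comes to 840, which would not change what follows). PJP incidence 0.7% to 2% in AIIRD patients overall (Background).

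**Inputs assumed.** True risk ratio (RR) 0.30; the risk and prescribing models below.

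**1. Expected events, before any drug effect.**
- 800 × 0.007 = 5.6 and 800 × 0.02 = 16.
- Per group, over four groups: 1.4 to 4.
- If half are treated and the RR is 0.30, the multiplier is (1 + 0.30)/2 = 0.65, giving 3.6 to 10.4 in all.

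**2. Stratification by the high/low class only.** Let *s* be a standard normal risk score cut at its median. PJP risk is proportional to 2^*s*, and the odds of intended prophylaxis double per SD. Let *m* be the mean untreated risk in a level, *u* the risk seen in controls and *t* the risk seen in treated patients. The true risk difference is 0.70*m*, so the NNT is inflated by 0.70*m*/(*u* − *t*). Numerical integration gives:

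| Comparison | *u* | *t* | RR seen | NNT ratio |
|---|---|---|---|---|
| No split | 0.786*m* | 0.364*m* | 0.463 | 1.66 |
| High level | 0.881*m* | 0.321*m* | 0.364 | 1.25 |
| Low level | 0.951*m* | 0.325*m* | 0.342 | 1.12 |

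If the odds halve per SD instead, the RR reads 0.247 (NNT × 0.87) in the high level and 0.263 (× 0.88) in the low level.

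On the log scale with the positive link, the bias is ln(0.463/0.30) = 0.434 without the split, 0.193 in the high level and 0.131 in the low level. The split removes about 55% and 70% of it.

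**3. Finer stratification.** The same model cut at the quartiles of *s* gives RRs of 0.327, 0.305, 0.305 and 0.341, with NNT ratios of 1.07, 1.02, 1.02 and 1.16. Most of the modelled bias goes. But four strata by two groups make eight cells, with 5.6/8 = 0.7 to 16/8 = 2 events each on average before any drug effect.

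**4. A factor outside the strata.** Stratification does nothing for a prognostic factor it does not use. Suppose half of a level carries such a factor.
- Risk × 3, prescribed to 70% with it and 30% without: *u* = 0.80*m*, *t* = 0.36*m*, RR 0.45, NNT × 0.70/0.44 = 1.59.
- Same factor, prescribing 30% and 70%: *u* = 1.20*m*, *t* = 0.24*m*, RR 0.20, NNT × 0.70/0.96 = 0.73.
- Weak case, risk × 1.5, prescribing 60% and 40%: *u* = 0.96*m*, *t* = 0.312*m*, RR 0.325, NNT × 0.70/0.648 = 1.08.

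**5. Chance.** With 4 control and 1.2 treated events, the SE of log RR is approximately √(1/4 + 1/1.2) = 1.04. That exceeds every log bias above, including ln(0.45/0.30) = 0.405.

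**The case against.** Four points can be made for the plan.

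- **Item 5c may control more than the high/low class.** It stratifies by risk factors, in the plural, and does not limit them to the two-level class. On a finer reading most of the modelled bias disappears (step 3). This stands: the 12–25% figure belongs to one reading. The finer reading, however, runs out of events.
- **Method details belong in the SAP.** The criterion for adjusting, the full covariate list and the model are commonly left there. This stands, and their absence is not the point. What the protocol itself fixes badly is that adjustment is optional. Reading 5a as also covering 5c leaves it optional in both.
- **Chance error is larger than the bias.** This also stands. But imprecision shows in an interval and confounding does not.
- **The protocol nowhere calls the groups non-randomised.** That is an inference from its silence and from grouping by intention, so the sponsor should confirm it.

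A reader might also infer confounding within risk levels from the Study design section, which says the study will "identify high-risk PJP populations among AIIRD patients and administer prophylactic trimethoprim-sulfamethoxazole (TMP/SMZ) treatment". The document does not support that. The sentence ties treatment to risk level, and comparing within level removes that link. No section says why prophylaxis is intended or withheld within a level.

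**Conclusion.** The point holds as a defect in the stated analysis. Groups formed by intended treatment, with no allocation method given, are to be compared for a causal objective under optional adjustment, and the NNT rests on stratification alone. This should be fixed.

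The size is illustrative. If stratification means only the high/low class, the graded-risk model leaves the NNT about 12–25% too large, or 12–13% too small if prescribing runs against risk. With four finer strata and the positive link the error is about 2–16%. A factor outside the strata could do less or more. All of this rests on the assumed RR of 0.30 and the assumed risk and prescribing models.

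The documents establish neither the size nor the direction of any bias, nor that one will occur. Confidence is high about the wording and much lower about how much bias would remain.

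**What to change.** **Item 5a.** Delete *if necessary*. Make a confounder-adjusted comparison of PJP incidence within risk level the main analysis. Fix the baseline factors before outcomes are examined, and include those the protocol already names: corticosteroid exposure, combined immunosuppressants, pulmonary disease, IgA and IgM, age and sex.

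**Item 5c.** Derive the NNT from the same adjusted risk difference and repeat the adjustment in each bootstrap resample. Keep the unadjusted result as descriptive. State which factors define the strata.

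**Item 3a.** Replace the reference to the intention-to-treat principle with a statement of how patients come to be in the prophylaxis or control group. Call the groups non-randomised if the sponsor confirms that.

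**Left to the SAP.** An adjustment method suited to few events, and the target population. The latter matters. With the × 3 factor of step 4 and an untreated risk of 2%, the whole-group NNT is 1/(0.70 × 0.02) = 71. Overlap weighting, with weights *e*(1 − *e*) for prescribing probability *e*, would give 92 if prescribing were 90% with the factor and 40% without, and 58 if it were 60% and 10%.

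**Cost.** Wording in three items, modest analysis work and somewhat wider intervals; how much wider depends on the method and on group overlap, which the protocol does not give. Unmeasured confounding and sparse events remain.
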